1.3.5. Safety, Efficacy, and Pharmacokinetic Parameters

1.3.5.1. Safety Parameters

The safety and tolerability of MT-3724 will be evaluated by means of drug related DLT, AE reports, physical examinations, and clinically significant changes in the laboratory safety evaluations. Adverse events will use the descriptions and grading scales found in the revised National Cancer Institute Common Terminology Criteria for Adverse Events (CTCAE) v4.03.

The evaluation of the MTD and DLT will be performed on all subjects enrolled in Part 1 of the main Core Study who receive at least one infusion of MT-3724. MTD is defined as the highest dose level at which $\leq 33\%$ (or 2/6) of subjects experience a DLT.

A DLT will be defined as a toxic effect that is presumed to be related to MT-3724 and considered unacceptable because of its severity and/or irreversibility and as such may limit further dose escalation. Dose-limiting toxicities will be defined based upon any toxic effects seen in the Core Study. Adverse events during Repeat Dosing will not be classified as DLTs. If a toxicity can be satisfactorily documented to be unrelated to MT-3724, then that specific toxicity will not be considered to impact the stopping or dose escalation rules.

A DLT will be determined as follows:

1. Grade 3 or greater AE: Any Grade 3 or greater adverse event that cannot clearly be determined to not be related to MT-3724 or disease progression will be considered to be a DLT.
2. Grade 3 or greater non-hematologic laboratory abnormality: Any Grade 3 or greater non-hematologic laboratory abnormality that fails to spontaneously recover to less than Grade 3 on retest prior to the next scheduled dose of MT-3724 or within 10 days (whichever is shorter) unless the event can be clearly determined to not be related to MT-3724 or tumor progression will be considered a DLT excepting the following:
 - Parameters for liver function test (AST, ALK, PT [INR], aPTT, Bilirubin, and Alk Phos) abnormalities to be considered a DLT are detailed in Section 1.3.3.
3. Grade 3 or greater hematologic laboratory abnormality: Because subject treated with anti-CD20 MAb develop Grade 3 or higher lymphopenia and because it is an expected pharmacodynamic effect of MT-3724, lymphopenia will not be considered a DLT.
 - Unless the event can be clearly determined to not be related to MT-3724 or disease progression changes in the following specific hematologic parameters will qualify as a DLT:
 - i. Febrile neutropenia (absolute neutrophil count $< 1000/\mu\text{l}$ and temperature $\geq 38.5^\circ\text{C}$)
 - ii. Grade 4 neutropenia for > 10 days
 - iii. Grade 3 thrombocytopenia with bleeding
 - iv. Grade 4 thrombocytopenia
 - v. Grade 4 anemia not due to underlying disease

For all other hematologic laboratory abnormalities, any grade 3 or greater hematologic toxicity that fails to spontaneously recover to less than grade 3 within 10 day (and prior to additional doses of MT-3724) unless the event can be clearly determined to not be related to MT-3724 or tumor progression will be considered a DLT.

4. A grade 2 (moderate) AE might invoke a stopping rule if:

- It is not pre-existing
- It is not due to disease progression
- It is not manageable with standard outsubject therapies AND
- It persists in the judgment of the Investigator(s) for an unreasonable people.

5. Any new Grade 1 (Mild) AE attributable to MT-3724 will not be considered a DLT.

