#### **4.1.1.1      Subject Evaluable for Dose Decisions**

Subjects in Part 3 will be evaluable for dose decisions if they satisfy one of the following criteria:

- Have had a DLT after at least one dose of MT-3724 in Cycle 1; or
- In the absence of toxicities that have delayed or caused omission of doses, subjects have received at least 4 of 6 (67%) doses of MT-3724 within 21 days

Subjects who are not evaluable for dose decisions will be replaced.

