Subjects will receive a single course of study drug via a 2 to 4 hour intravenous (IV) infusion of MT-3724 on Days 1, 3, 5, 8, 10 and 12. The first dosing cohort will receive 5 micrograms per kilogram (mcg/kg) per dose of MT-3724. Each cohort is planned to have from 3 to 6 subjects, but additional subjects may be added to one or more dosing cohorts to further explore safety and/or efficacy signals. Following the first dose in the Core Study, there will be a minimum 28-day observation period for each subject to document safety and tolerability prior to initiating any additional treatment cycles in the Repeat Dosing Study (see below). Subjects experiencing a dose limiting toxicity (DLT) in the Core Study (Days 1-28) must be withdrawn from the study and receive no further doses of MT-3724. Subjects will have successfully completed the Core Study if they receive at least 4 of the 6 infusions in their first cycle and they are followed for 28 days after their first dose. If a subject in the Core Study completes less than 4 of the 6 infusions in the first 12 days and the missed infusions were not due to an MT-3724-related DLT or AE that contraindicates further dosing then the Investigator in consultation with the Sponsor may attempt to achieve a minimum 4 infusions by administering the missed doses in the third week (Days 15 - 19) of the Core Study. In such instances, subjects must still be observed for 28 days following the first dose in the Core Study prior to initiating any further study drug dosing.

Following Data Monitoring Committee (DMC) safety review and approval to escalate, the subsequent cohorts are planned to be dosed at 10, 20, 50, 100, 150, and 200 mcg/kg/dose.

- **Dose Escalation:** Additional dose cohorts may be added above the 200 mcg/kg/dose cohort if (1) less than two DLTs are observed at the completion of that cohort's first cycle and (2) maximum PK/PD parameter changes have not yet been observed. The incremental increases of cohorts beyond 200 mcg/kg/dose/day will be determined by the PK/PD observations and all safety data.

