- **Dose-De-escalation:** Additional cohorts at dose levels below an identified toxic dose level will be added to more accurately identify the MTD. At the identification of the first dose cohort that has > 33% DLTs, the maximal administered dose, an interim cohort will be added at a dose that is approximately 25 mcg/kg/dose lower than the maximal administered dose. If that lower dose has > 33% DLTs then the next highest cohort by a further 25 mcg/kg/dose reduction will be studied. For example, if there are > 33% DLTs at the 150 mcg/kg/dose, it will become the maximal administered dose and a 125 mcg/kg/dose cohort will be added. If the 125 mcg/kg/dose cohort has > 33% DLTs then the next lowest dose cohort (100 mcg/kg/dose in this example) will be expanded to 6 subjects if not previously done. Cohorts will be explored at ~25 mcg/kg/dose reductions until the MTD has been identified by documenting < 33% DLTs in a cohort expanded to the required 6 subjects. If the MTD cohort identified in the Core Study is expanded beyond 6 subjects for further PK, PD and/or efficacy exploration then from their first cycle, the subjects added to this expansion cohort will be dosed according to the Repeat Dosing 21-day cycle.

Part 1 Repeat Dosing (Cycles 2-5)

Following successful completion of the 28-day Core Study of Part 1, subjects may continue to receive up to 4 more cycles of treatment as long as they have experienced no AE attributable to MT-3724, which would contraindicate further dosing and provided their disease has not progressed.

If a subject has tolerated repeat cycles of MT-3724 without evidence of a toxicity that would prohibit further dosing or evidence of disease progression, but their dose is subsequently determined to be above the MTD, he/she may continue to receive additional cycles at the highest studied dose in Part 1 that has been confirmed to be below the MTD or at the dose confirmed to be the MTD.

Part 2

Up to 40 subjects will be enrolled in Part 2. Subjects may be enrolled and treated simultaneously through competitive enrollment at multiple study centers in North America and Europe.

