2.3.1. Main Study

Part 1: If a subject terminates study participation prior to per protocol Core Study completion the Investigator or their representative should notify Molecular Templates and the CRA immediately. In all cases, the reason for withdrawal must be recorded in the eCRF and in the subject's medical records. If the reason is not known, the subject must be followed to establish whether the reason was an AE, and, if so, this must be recorded. If a subject withdraws for reasons other than a DLT and prior to completing the Core Study Molecular Templates and the CRA must be informed immediately so a timely decision can be made regarding replacement of the subject. If a subject withdraws because of disease progression prior to completion of the Core Study, Molecular Templates and the CRA must be informed immediately so a timely decision can be made regarding replacement of the subject. Subjects in any cohort will not be replaced if they are withdrawn because of a DLT in the Core Study or they are withdrawn because of an AE or disease progression in the Repeat Dosing Study.

Part 2: If a subject terminates study participation prior to per-protocol post-Cycle 2 tumor assessment for any reason other than progressive disease, the Investigator or their representative should notify Molecular Templates and the CRA immediately. In all early withdrawal cases, the reason for withdrawal must be recorded in the CRF and in the subject's medical records. If the reason is not known, the subject must be followed up to establish whether the reason was an AE, and, if so, this must be recorded. If a subject terminates study participation prior to per-protocol post-Cycle 2 tumor assessment for any reason other than progressive disease, the Investigator or their representative should notify Molecular Templates and the CRA immediately. The DMC must review the study data from any subject who withdraws from the study prior to completing at least eight of twelve infusions in Cycles 1 and 2 and completing the post-Cycle 2 tumor reassessment. If withdrawal is for any reason other than disease progression, the DMC must review all safety data available for that subject and determine if the subject should be replaced in the MTD expansion cohort.

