3.9. Withdrawals, Dropouts, Loss to Follow-up

Subjects withdrawing from a cohort in Part 1/Core Study for reasons other than a DLT will be replaced. Subjects participating in Part 2 (MTD Expansion) who are withdrawn any time before Day 21 due to disease progression will be replaced. Subjects participating in Part 2 who withdraw prior to completion of the post-Cycle 4 tumor reassessment may be replaced at the Sponsor's discretion.

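### The SAP's Part 1 DLT denominator keeps treated subjects who withdrew without a DLT and were replaced, so the DLT rate behind the MTD can only be biased downward

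*SAP*

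**What the plan says.** SAP 1.3.5.1 (Safety Parameters) names the set for the MTD and DLT evaluation: "all subjects enrolled in Part 1 of the main Core Study who receive at least one infusion of MT-3724". It then defines the MTD as the highest dose level at which at most 33% of subjects have a DLT, and equates that limit with 2/6.

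SAP 1.3.1.1 (Main Study) words the limit differently. There the MTD is identified by "documenting < 33% DLTs in a cohort expanded to the required 6 subjects". The same section gives a standard for adequate observation: "Subjects will have successfully completed the Core Study if they receive at least 4 of the 6 infusions in their first cycle", and they must also be followed for 28 days after the first dose. That standard is not linked to the DLT evaluation.

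Replacement is covered twice. SAP 3.9 is categorical: "Subjects withdrawing from a cohort in Part 1/Core Study for reasons other than a DLT will be replaced". SAP 2.3.1 instead asks that the sponsor be told of a non-DLT withdrawal or a withdrawal for progression "so a timely decision can be made regarding replacement of the subject". For DLTs, SAP 2.3.1 says: "Subjects in any cohort will not be replaced if they are withdrawn because of a DLT in the Core Study".

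SAP 2.1 defines a Safety Set, a Pharmacokinetic Analysis Set and a Full Analysis Set, but no DLT-evaluable set. For Part 3 the current protocol has such a rule. Section 4.1.1.1 counts a subject if a DLT occurred or if at least 4 of 6 doses were received within 21 days, and adds: "Subjects who are not evaluable for dose decisions will be replaced".

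**The concern.** A DLT rate is meant to describe subjects who were given enough of the regimen, and watched for long enough, to show a DLT. A subject who stops after one of six infusions has had a fraction of the exposure being judged. Some DLT criteria in SAP 1.3.5.1, such as Grade 4 neutropenia lasting more than 10 days, also need sustained follow-up.

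Under the SAP, subjects who leave with a DLT are not replaced and count in both numerator and denominator. Subjects who leave without one are replaced (or may be), yet as treated subjects they remain in the denominator as DLT-free. The selection works in one direction only. The resulting set also no longer matches the cohort of six that both threshold wordings imply.

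SAP 1.2 says that this plan is the basis for the results sections of the clinical study report, so the denominator governs how the Part 1 DLT evidence is presented. Protocol 6.1.1.1 still cites an MTD identified in Parts 1 and 2 as the ceiling for the step-up regimen, so that evidence remains in use.

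**Working it through.** **Inputs.** Denominator: all treated Part 1 Core Study subjects (SAP 1.3.5.1). Cohort size: 6 (SAP 1.3.1.1, and the 2/6 in 1.3.5.1). Limit: at most 33%, equated with 2/6 (1.3.5.1), or strictly below 33% (1.3.1.1). The number *k* of treated, replaced, DLT-free subjects at a dose level is not in the documents; *k* = 0 to 4 is an assumption.

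**The plan's own figure.** 2/6 = 0.3333, which is 33% after rounding. Taken literally, 0.3333 is above 0.33, but the 2/6 in 1.3.5.1 settles that two of six qualifies there. Under the wording in 1.3.1.1, two of six does not qualify.

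**Effect on the rate.** With *d* DLTs among six adequately observed subjects, the rate on the all-treated set is *d* / (6 + *k*).

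| *k* | 2 DLTs | 3 DLTs |
|---|---|---|
| 0 | 2/6 = 33.3% | 3/6 = 50.0% |
| 1 | 2/7 = 28.6% | 3/7 = 42.9% |
| 2 | 2/8 = 25.0% | 3/8 = 37.5% |
| 3 | 2/9 = 22.2% | 3/9 = 33.3% |
| 4 | 2/10 = 20.0% | 3/10 = 30.0% |

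For two DLTs, one replaced subject lowers the rate by 14% in relative terms (1 − 6/7) and two lower it by 25% (1 − 6/8). With no DLTs there is no effect.

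**Effect on the MTD rule.** Let *r* be the largest DLT count that satisfies the limit at *N* = 6 + *k*. If DLTs arise only in the six adequately observed subjects, each with true probability *p*, the chance that the dose level satisfies the rule is P(X ≤ *r*), with X binomial(6, *p*).

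- *Strictly below 33% (1.3.1.1).* At *k* = 0, *r* = 1. At *k* = 1, *r* = 2, because 2/7 = 28.6%. One replaced subject is enough to change the outcome. At *p* = 0.40 the chance of passing rises from 23.3% to 54.4%.
- *At most 33%, or 2/6 (1.3.5.1, limit read as one third).* At *k* = 0, 1 and 2, *r* = 2, so one or two replaced subjects change nothing. At *k* = 3, *r* = 3, because 3/9 = 33.3%. At *p* = 0.40 the chance of passing rises from 54.4% to 82.1%; at *p* = 0.50 it rises from 34.4% to 65.6%.

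**Restricting the denominator.** If only subjects with a DLT or a completed Core Study count, *N* returns to 6: two DLTs are 33.3% and three are 50.0%, whatever *k* is.

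**The case against.** The strongest reply is that the SAP can be read as working with a fixed cohort. The 2/6, the required six subjects, the standard 3+3 design in SAP 3.1 and the word replaced itself all suggest that a replacement takes over the withdrawn subject's place in the count. That is how a 3+3 cohort might well be run. But the SAP never says so, and its only explicit statement of the set is all treated subjects. The fixed-cohort wording therefore shows a conflict within the SAP; it does not resolve it.

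Several other objections stand and limit the point.

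- A reader might infer that one replaced subject moves a two-DLT cohort across the limit in every case. Under SAP 1.3.5.1 two of six already qualifies, so nothing moves. The crossing at one subject belongs only to the wording in 1.3.1.1.
- A reader might infer that early withdrawals had no chance to show a DLT. SAP Table 1 requires Visit 8 (Day 16-19) and Visit 9 (Day 23-25) even after early withdrawal, so exposure and the chance of a DLT are reduced, not nil.
- SAP 1.3.5.1 sits in a section that restates the protocols. The planned safety outputs in SAP 4.6.1 include a listing of TEAEs declared as DLTs, but name no table of DLT rates.
- The protocol's Part 3 rule covers a different regimen with a 21-day DLT window, and this SAP does not cover Part 3. It is a useful precedent, not evidence of contradiction.

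**Conclusion.** The point holds as a one-directional bias in the stated denominator. Followed as written, the SAP can only understate the DLT rate at a dose level that has at least one DLT and at least one treated, replaced, DLT-free subject. With two DLTs, 33.3% becomes 28.6% or 25.0% with one or two such subjects. A change in whether the limit is met needs one replaced subject under the wording in 1.3.1.1, or three DLTs with three replaced subjects under that in 1.3.5.1.

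The actual size is unknown and may be zero. The documents give neither the number of replaced subjects nor the DLT count per cohort, and SAP 2.3.1 leaves it open whether every such subject was replaced.

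A reader might go further and infer that the Part 1 MTD was set too high for this reason. The documents do not support that. SAP 1.2 states that Part 1 was complete when this version was written, and SAP 1.2.1.1 records an MTD of 75 mcg/kg/dose that was then adjusted downward to 50 because of safety concerns. What is affected is the reporting and support of the Part 1 DLT rate and MTD. That is worth correcting, but it is not shown to have altered a dose decision.

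**What to change.** In SAP 2.1 and 1.3.5.1, define a DLT-evaluable set: Part 1 subjects who had a DLT in the Core Study, or who completed it as SAP 1.3.1.1 defines completion (at least 4 of 6 infusions and 28 days of follow-up). Use it as the denominator for the MTD evaluation and for any DLT rate that is reported. Keep the Safety Set for all other safety outputs. List the treated subjects left out, with reasons; SAP 4.1 already tabulates reasons for exclusion by population.

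Reconcile two pairs of statements: the threshold in 1.3.5.1 (at most 33%, or 2/6) with that in 1.3.1.1 (below 33%), and automatic replacement in 3.9 with replacement by decision in 2.3.1.

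The cost is one additional population definition and possibly a slightly higher reported DLT rate. If every treated subject either had a DLT or completed the Core Study, no number changes and the ambiguity is closed.

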1.3.5.2. Efficacy Parameters

As this is a dose finding study and is designed to assess the safety and tolerability of MT-3724, all efficacy analyses are exploratory in nature, based on documented tumor responses.

Tumor response following completion of even numbered (e.g., 2, 4, etc.) courses of MT-3724 and at final safety assessment following termination of MT-3724 will be assessed according to the Tumor Response Criteria for malignant lymphoma ([Cheson et al 2007](#)) defined by the International Working Group.

In addition, source document verified tumor lesion measurement data that was not reported in the EDC was collected and tallied by the Sponsor via an Excel Spreadsheet. The data in this Spreadsheet will be used for the analysis of percent change in tumor size.

Endpoints will include:

- Best Overall Response.
- Objective response rate (ORR) - Objective response will be determined as the proportion of subjects with either CR or PR using the tumor response criteria described below.
- Disease Control Rate (DCR) will be calculated as the proportion of subjects who achieve either CR, PR or stable disease status.
- Duration of tumor response (DOR) - Duration of response is defined as the time from the first occurrence of either complete or partial response to first documented evidence of disease recurrence or progression. Subjects without evidence of progression will be censored at time of last disease assessment. Only responders (CR or PR) will be included for this analysis.
- Progression-free survival (PFS) – Progression-free survival is calculated from the date of first infusion of MT-3724 to first documented evidence of disease recurrence or progression or death due to any cause. Subjects who are last known to be alive and without evidence of progression will be censored at time of last disease assessment.
- Duration of stable disease (i.e., duration of disease control) - Duration of at least stable disease is defined as the time from the date of first infusion of MT-3724 to first

documented radiologic evidence of disease recurrence or progression. Subjects without evidence of progression will be censored at time of last disease assessment.

- Overall survival (OS) – Overall survival is calculated from the date first dose of study treatment to the date of death. Subjects who are still alive prior to the data cutoff for final efficacy analysis, or who dropout prior to study end, will be censored at the day they were last known to be alive.
- Percent change from baseline in lesion size based on the Sum of the Product of Diameters (SPD).

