## 3.2 Part 4 Objectives and Endpoints

OBJECTIVES	ENDPOINTS
Primary	

 
To determine the efficacy of MT-3724 as monotherapy in subjects with relapsed or refractory DLBCL based on the ORR by the Lugano Classification for Lymphoma (Cheson, 2014)
 
	
 
overall response rate is defined as the proportion of subjects with either a CR or a PR as determined by independent, blinded central review
 

Key Secondary	

 
To determine additional measures of efficacy of MT-3724 as monotherapy in subjects with relapsed or refractory DLBCL
 
	
 
Duration of tumor response, defined as time from initial documentation of tumor response (complete response [CR] or partial response [PR]) to disease progression
 

Secondary	

 
To determine the safety of MT-3724 as monotherapy in subjects with relapsed or refractory DLBCL
 
	
 
adverse events
 
laboratory abnormalities
 
vital signs
 

 
To evaluate the effect of MT-3724 on the QT/QTc interval in subjects with relapsed or refractory DLBCL
 
	
 
electrocardiograms (ECGs)
 
adverse events suggestive of cardiotoxicity
 

 
To determine additional measures of efficacy of MT-3724 as monotherapy in subjects with relapsed or refractory DLBCL
 
	
 
overall response rate, defined as the proportion of subjects with either a CR or a PR as determined by investigator assessment
 
disease control rate (DCR), defined as proportion of subjects who have achieved CR, PR and SD (defined as SD for 6 months or longer)
 
progression-free survival (PFS), defined as the time from study enrollment to the earliest date of disease progression or death from any cause
 
overall survival (OS), defined as the time from study enrollment to death from any cause
 

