### 9.3.2.2 Secondary Efficacy Variables

The secondary efficacy variables will be PFS, DCR, DOR and OS. All secondary efficacy variables will be determined from the radiological tumor scans according to the Lugano Classification for Lymphoma ([Cheson, 2014](#)) relative to the FAS population.

Secondary efficacy variables will be evaluated separately for Parts 3 and 4.

The DCR will be defined as the percent of subjects with objective response of CR, PR, or SD, (defined as SD for 6 months or longer). The DCR will be analyzed using similar methods as the ORR.

For subjects who continue to receive treatment after radiographic PD, and have confirmed PD at next assessment, the time of PD will be that of the first detection.

The DOR will be defined as the time from the first documented objective response (CR or PR) to the date of PD or death from any cause. Subjects who have not progressed at the time of data base lock will be censored at the date of their last tumor assessment.

The PFS will be defined as the time from the start of treatment with MT-3724 on C1D1 to the date of PD or death from any cause. Subjects who have not progressed at the time of data base lock will be censored at the date of their last tumor assessment.

For both DOR and PFS, those subjects who have no data on progression (eg, subjects who discontinued the study due to other reasons than progression and who were not followed up until progression) and/or have no data on tumor assessment after baseline and are still alive will be censored at the subject's date of first dose.

The OS will be defined as the time from the start of treatment with MT-3724 until death from any cause.

The DOR, PFS and OS will be summarized descriptively using the Kaplan-Meier methods (K-M median and corresponding 95% CI, quartiles, number of events, number censored, Kaplan-Meier figure). Since these methods assume missing data are missing at random, supportive analyses will be conducted assuming data are missing not at random.

As a secondary sensitivity analysis for efficacy (eg, study drug exposure, lines of prior therapy, DOR to prior therapy, subject subsets), the mFAS population will be utilized. The same statistical techniques will be applied on each efficacy endpoint on the mFAS population.

Data listings will be created to support each analysis and to present all efficacy data.

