1.2. Study Objectives

This statistical analysis plan (SAP) contains detailed information on definitions of analysis populations, derived variables, and statistical methods for the analysis of safety and efficacy data from the Phase I/ Ib clinical studies: MT-3724_NHL_001_US and MT-3724_NHL_001_EXT_US. The statistical analyses and summary tabulations described in this SAP will provide the basis for the results sections of the clinical study report (CSR) for this trial. This SAP will also outline any differences in the currently planned analytical objectives relative to those planned in the study protocol.

The SAP is based upon the following study documents:

- Study protocols v7.0 dated 08 February 2018 for MT-3724_NHL_001_US and v2.0 dated 16 April 2016 for MT-3724_NHL_001_EXT_US.
- Electronic Case Report Form (eCRF), v10.0 dated 16 May 2018.

Although Part 1 of this study allows for the enrollment of subjects with NHL or Chronic Lymphocytic Leukemia (CLL), at the time of writing this SAP there are no plans to enroll subjects with CLL, as Part 1 of this study is complete. No subject with CLL were enrolled in Part 1.

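### Protocol v11.0 ends duration of response at progression alone in its endpoint tables but at progression or death in section 9.3.2.2, and the Parts 1 and 2 SAP's progression-only rule censors responders who die

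*SAP*

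**What the plan says.** **Protocol v11.0, endpoint tables.** Section 3.2 lists DOR as the key secondary endpoint of Part 4: "Duration of tumor response, defined as time from initial documentation of tumor response (complete response [CR] or partial response [PR]) to disease progression". The synopsis (1.1) uses the same end event for Parts 3 and 4, and section 3.1 uses it for Part 3, where DOR is a secondary endpoint.

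**Protocol v11.0, section 9.3.2.2.** The analysis section for Parts 3 and 4 runs DOR from the "first documented objective response (CR or PR) to the date of PD or death from any cause". Subjects who have not progressed by database lock are censored at their last tumor assessment, and the synopsis paragraph on efficacy endpoints has a similar rule. Neither sentence requires the subject to be alive. That condition appears only in a separate 9.3.2.2 sentence on subjects who lack progression data or a post-baseline scan.

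**SAP, section 1.3.5.2.** DOR is measured "from the first occurrence of either complete or partial response to first documented evidence of disease recurrence or progression", and "Subjects without evidence of progression will be censored at time of last disease assessment". In the same list, progression-free survival (PFS) runs "to first documented evidence of disease recurrence or progression or death due to any cause", and only subjects last known to be alive and progression-free are censored.

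**Scope of the SAP.** SAP section 1.2 names as its basis "Study protocols v7.0 dated 08 February 2018 for MT-3724_NHL_001_US" together with the extension protocol. It covers Parts 1 and 2 and the extension, and says that "all efficacy analyses are exploratory in nature".

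**The concern.** An analyst building the Part 4 DOR from protocol v11.0 could follow the tables or section 9.3.2.2 and, in either case, cite current text. The two choices treat a responder who dies without documented progression differently. Under one, the response ends at death. Under the other, the subject leaves the risk set at the last scan, and the Kaplan-Meier curve treats that subject as someone whose response might have continued.

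Such deaths are plausible. Protocol 2.2.1 reports a fatal capillary leak event in Part 3 (it does not say whether that subject had responded). Protocol 2.1.3 cites an overall survival of 6.3 months in refractory disease. Scans are 6 weeks apart in protocol v11.0. Under the SAP, response is assessed after even-numbered cycles of at least 21 days, so 2 × 21 = 42 days or more apart. A subject can die between scans.

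At stake is how durable the responses appear. In a single-arm trial, DOR is read next to the response rate, and a rule that censors deaths can only make it look the same or longer.

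**Working it through.** **1. Is there a stated figure to reproduce?** No. Neither document gives a median DOR, a DOR event count or power for DOR. The only powered figure is the Part 4 response test (at least 23 of 88, 17% against 32%). It reproduces: exact one-sided alpha 0.0201 and power 0.9039, against the stated below 0.025 and 90.4%. It does not depend on how DOR is defined.

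**2. What happens to a responder who dies without documented progression?**

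| Source | End event includes death? | Censoring limited to the living? | Result for this subject |
|---|---|---|---|
| Protocol 1.1, 3.1, 3.2 | No | Not stated in the tables | Not an event |
| Protocol 9.3.2.2 | Yes | No, in its general rule | Event by the definition, though the censoring sentence taken literally also applies |
| SAP 1.3.5.2, DOR | No | No | Censored at last assessment |
| SAP 1.3.5.2, PFS | Yes | Yes | Event |

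The SAP's PFS bullet shows that its authors named death where they meant to count it, so its absence from the DOR bullet cannot be read as shorthand.

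**3. Direction and size.** Let λp be the hazard of progression, λd the hazard of death without progression, both constant, and q = λd/(λp + λd).

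- Death counted: median = ln 2/(λp + λd).
- Death censored: median = ln 2/λp.
- Ratio = (λp + λd)/λp = 1/(1 − q).

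The documents give no q. Over an assumed range, with an illustrative 6-month median when deaths are counted:

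| q (assumed) | 1/(1 − q) | Median with deaths censored |
|---|---|---|
| 0% | 1.00 | 6.0 months |
| 5% | 1.05 | 6.3 months |
| 10% | 1.11 | 6.7 months |
| 20% | 1.25 | 7.5 months |
| 30% | 1.43 | 8.6 months |

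For scale, if all 23 responders at the rejection boundary reached an end event, q of 10%, 20% and 30% would be about 2, 5 and 7 deaths (23 × 0.1 = 2.3; 23 × 0.2 = 4.6; 23 × 0.3 = 6.9).

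**4. Effect of the scan schedule.** The formula assumes continuous observation. A simulation (200,000 responders per setting, scans every 6 weeks, the same 6-month underlying median, deaths either counted or censored at the last scan) gave:

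| q (assumed) | KM still in response at 6 months: deaths counted / censored | Observed KM median, months: counted / censored |
|---|---|---|
| 0% | 0.53 / 0.53 | 6.9 / 6.9 |
| 5% | 0.53 / 0.55 | 6.9 / 6.9 |
| 10% | 0.53 / 0.56 | 6.9 / 6.9 |
| 20% | 0.52 / 0.60 | 6.9 / 8.3 |
| 30% | 0.52 / 0.64 | 6.9 / 9.7 |

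The curve shifts upward at every q above zero. The observed median can move only in steps of one scan interval when progression drives it, so here it does not change at 5% or 10% and jumps at 20% and 30%.

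**The case against.** **The SAP does not govern Part 4.** A reader might infer that the SAP breaches protocol 9.3.2.2. The documents do not support that. The SAP rests on protocol v7.0, has no Part 3 or 4 cohorts and uses the 2007 response criteria. Section 9.3.2.2 belongs to v11.0 and to Parts 3 and 4, for which protocol section 9 announces a SAP. The v7.0 text is not supplied, so whether the SAP departs from its own protocol cannot be checked. This objection stands in full.

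**The statistical section already has the right rule.** Section 9.3.2.2 counts death and plans supportive analyses for data missing not at random. That helps, but nothing says it overrides the endpoint tables. A supportive analysis also does not settle what the main estimate is.

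**Progression-only DOR is a legitimate estimand, and deaths remain visible in PFS and overall survival.** Both are true, and where the SAP applies efficacy is exploratory. This lowers the weight of the SAP part. It does not justify two definitions for one key secondary endpoint, and a DOR that censors deaths needs to be labelled as such.

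**The inflation figures are hypothetical.** They are: q is assumed, and the effect is zero if no responder dies without documented progression.

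**Duration of stable disease.** A reader might want death added there too, because it has the same gap. It already starts at first infusion, so adding death would essentially reproduce the SAP's PFS. That change is not recommended.

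**Conclusion.** The point holds as an internal contradiction in protocol v11.0 on the Part 4 key secondary endpoint: three places end DOR at progression, one at progression or death. The Parts 1 and 2 SAP shares the progression-only form and, read as written, censors responders who die. That is a lesser matter, because its efficacy analyses are exploratory.

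The direction of the effect is clear: censoring these deaths tends to overstate DOR. Its size is not known from the documents. The median ratio of 1.05 to 1.43 rests on an assumed q of 5% to 30%, constant hazards and continuous observation. With 6-weekly scans the observed median may not move at small q although the curve does. The primary response test is unaffected.

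**What to change.** 1. In protocol 1.1, 3.1 and 3.2, define DOR as in 9.3.2.2, ending at progression or death, whatever the cause.
2. In 9.3.2.2 and the synopsis, state for DOR that only subjects who are alive without progression are censored at the last tumor assessment.
3. Carry that single definition and censoring rule into the Parts 3 and 4 SAP.
4. In the Parts 1 and 2 SAP, section 1.3.5.2, count death as a DOR event. At the least, state how deaths without documented progression are handled and report a sensitivity analysis that counts them. Leave duration of stable disease as it is.

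The cost is wording. Deaths are already collected for overall survival, so no new data are needed. The reported DOR may be shorter, by more than a little if deaths without documented progression are common.
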